| EAR | Estimated average requirement |
| EP | |
| FII | Food insulin index |
| GI | Glycemic index |
| GL | Glycemic load |
| iAUC | Incremental area under the curve |
| IUC | Inter-university cooperation |
| JKUAT | Jomo Kenyatta University of Agriculture and Technology |
| KEMRI | Kenya Medical and Research Institute |
| KU Leuven | University of Leuven |
| LCEFoNS | Legumes Centre of Excellence for Food and Nutritional Security |
| MoH | Ministry of Health |
| NACOSTI | National Commission for Science, Technology and Innovation |
| CoV | Co-efficient of variance |
| SEM | Standard error of means |
| SOP | Standard operating procedure |
| T2DM | Type-2 diabetes mellitus |
| VAS | Visual analog sales |
| VUB | University of Brussels |

1. INTRODUCTION/BACKGROUND

Kenya is classified as having three main forms of malnutrition: overweight, anaemia and stunting [1], exhibiting a double burden of malnutrition nutritional landscape [2]. Indicators of overweight and obesity, and diabetes in both adult men and women either show no progress or are worsening when looking at trends from the 80's to present [3]. Iron and zinc, whose deficiencies (acute or chronic) manifest as iron deficiency anaemia and stunting are micronutrients of public health concern in Kenya [4]. Type-2 diabetes is one of the priority non-communicable diseases (NCDs) [5] in Kenya with a prevalence of 5.8% and 6.2% in men and women [6].

Type 2 diabetes (T2DM) is the most common form of diabetes. It is a chronic metabolic disease occurring when the pancreas is unable to produce sufficient amounts of insulin or when the body cannot effectively utilize produced insulin, or both. Insulin regulates the amount of glucose in blood and T2DM is characterized by hyperglycemia [7]. Diabetes due to its nature has an inflammatory disease character, with higher inflammatory processes as a result of diseases duration and glycemic control [8]. Iron homeostasis is affected by hepcidin levels. Hepcidin levels are abnormally high during inflammation, resulting in a decrease in iron uptake in the gut [9]. Investigators have observed positive associations between serum ferritin and blood glucose levels, body mass index (BMI) and lipid profiles [11, 12]. This suggests that the incidence of anemia is likely to increase in poorly controlled diabetes. Therefore, reducing blood glucose levels could help reduce the risk of anemia in diabetic populations. Zinc is found in highest concentrations in the pancreatic β -cell in the human body [12]. Dysregulation of zinc is known to occur in both type 1 and type 2 diabetes. However there is no conclusive evidence as to whether zinc deficiency causes the diabetes or is merely a consequence of the disease [13]. Suggested potential beneficial mechanisms of action of zinc among diabetes patients are its antioxidant role. Studies have reported the association of high zinc levels with reduced oxidative stress (lowering lipid peroxidation [14], chronic hyperglycemia, insulin resistance and β -cell loss [15]).

We conducted a baseline study during quarter 4, 2018 in Makeni County to study the double burden of malnutrition at the individual level in T2DM (N=168). Preliminary reports from the study show anaemia as present in 34.4% and 24.8% in men and women respectively. 142 participants had a random blood sugar of $>8.5\text{mmol/L}$. 72.2% of the participants were also

hypertensive (reported current use of hypertension medication). Diets consumed were characterized by low sources of readily bioavailable iron and zinc. Diet quality is at the core of both diabetes management and the double burden of malnutrition. From the daily consumption data, we found the intake of both iron and zinc to be lower than their respective estimated average requirement (EAR). Further considering the characteristic low bioavailability diet, improvements in the quality of diets among this population is thus crucial.

This study aims to study the associated glucose, insulin and appetite responses associated with the consumption of a novel common bean product. This product profiling is key to inform dietary management of T2DM patients using this specific product.

2. PROBLEM STATEMENT AND JUSTIFICATION

Problem Statement

Though prevalence of T2DM in Makueni County is unknown, a high number of diabetes-related outpatient morbidity cases has been reported [16]. The double burden of malnutrition at the individual level has hardly been little studied and is less well understood than the prevalence of the double burden of malnutrition observed at country or household level.

Zinc is found in very high concentrations in pancreatic beta-cells [17]. Low zinc levels have been reported elsewhere among diabetes patients as compared to non-diabetic patients [18]. Associations between dysregulation in zinc homeostasis and pancreatic beta-cell function has been suggested [19]. Evidence is however still inconclusive as to whether zinc deficiency causes the disease or is a consequence of the disease [15]. Studies suggest that inflammatory state associated with obesity lead to alterations in iron homeostasis. However, work on iron metabolism during inflammation has been focused on studies on obesity combined with anemia in women, or in persons undergoing bariatric surgery [20, 21]. The metabolic basis and complications associated with T2DM result in dysregulation in zinc, iron and copper homeostasis. Dietary management of T2DM has concentrated on macronutrient consumption[22, 23].

Problem justification

Micronutrients are cofactors in β -cell function, glucose metabolic pathways, and in insulin signaling. Baseline data shows us inadequate mean daily zinc and iron intakes in a characteristic low bioavailable diet. Additionally, presence of anaemia was >20% in T2DM patients in Makueni,

Kenya (N=168). The successes and challenges of diet and food-based approaches have been addressed before [24]. Despite the knowledge that several nutrients are implicated in glycaemic control: 1) limited studies and evidence on micronutrient status among T2DM patients in Kenya is available, and, 2) limited evidence on targeted improved micronutrient consumption has been conducted in Kenya. To tackle both, micronutrient deficiency and metabolic health a new common bean product has been developed. We hypothesize that the newly developed product will have improved micronutrient bioaccessibility and that it will evoke desirable satiation and metabolic responses. Additionally, common beans contain soluble and insoluble fibre, phytonutrients and slowly digestible starch which are beneficial to glycaemic and lipaemic control.

3. REVIEW OF LITERATURE

3.1 Double burden of malnutrition at the individual level

T2DM in Kenya is on a rise with about 458,900 people diagnosed in 2017 and a 2.5 fold projected increase [25]. It is one of the NCDs accounting a big proportion of NCD-related mortality[26]. Risk factors of T2DM in Kenya are: age, physical inactivity, adoption of unhealthy lifestyles [5, 20]. Chronic hyperglycemia associated with T2DM results either in production of reactive oxygen radicals and/or compromises the antioxidant defense system activity [28]. In T2DM patients, zinc improves oxidative stress by a plethora of mechanisms: reducing chronic hyperglycemia, acting as a cofactor of the superoxide dismutase enzyme [29], regulating glutathione metabolism and metallothionein expression [30], and promoting phosphorylation of insulin receptors[31]. Copper is a necessary pro-oxidant for the catalytic activity of superoxide dismutase [32]. Zinc and copper are important for balanced redox mechanisms. Imbalances in redox mechanisms may contribute to diabetic complications. The importance of antioxidant nutrients in the management of this disease should be further explored.

Dysregulation of iron homeostasis is closely linked to the body's inflammatory response and T2DM. As yet, the link between dietary iron and metabolic dysfunction is incompletely understood [25, 26]. Hepcidin controls dietary iron absorption and distribution in metabolic tissues. Hepcidin binds ferroportin in iron storage tissues inhibiting export of iron. Several studies have found high ferritin levels in T2DM patients. In enterocytes, inhibition of ferroportin reduces the absorption of dietary iron into the blood by trapping it within the enterocyte [35]. With both iron deficiency and

overload associated with metabolic disorder, it is important to maintain iron levels within a narrow physiological range.

3.2 Nutritional profile of common beans

Several studies report that common bean is a food with a high content of proteins, carbohydrates, diet fiber, minerals and vitamins [36]. Depending on the common bean variant, protein ranges between 14% and 33%. They contain amino acids such as lysine, phenylalanine and tyrosine. They lack in methionine and cysteine (sulphur amino acids). Beans contain slowly digestible carbohydrates and a high proportion of non-digestible carbohydrates. Fiber (soluble and non-soluble) in beans would be beneficial to T2DM patients by reducing macronutrient absorption, satiety increase, increased sensibility to insulin, effects on inflammatory markers and on intestinal microbiota [37]. Common beans are important sources of iron and zinc. Moreover, they contain several bioactive compounds (anthocyanins, condensed tannins [38] and flavonoids [39]) possessing anti-inflammatory, antioxidant and other biological activity [40]. Due to their composition and effects, common beans have attractive properties for T2DM patients.

3.3 Estimated Average Requirements (EARs) for Zinc, Iron and Copper

The EARs for zinc, iron, and copper differ depend on age, body weight, sex, for pregnant and/or lactating women and on the bioavailability of the nutrient in a diet. Based on these factors approximate EAR values for adults' ≥ 18 years and ≥ 70 years are shown in **Table 1** below:

Table 1: Zinc, Iron and Copper EAR Summary, Ages 18 years and older

| Micronutrient | Male | Female |
|------------------------------|-----------|-----------|
| Zinc(mg/day) | 8.5 – 9.4 | 6.8 – 7.3 |
| Iron (mg/day) | 6 – 7.7 | 5 – 8.1 |
| Copper ($\mu\text{g/day}$) | 685 - 700 | 685 - 700 |

Source: adopted from Institute of Medicine (US) Panel on Micronutrients (2001)

It is important to remember that dietary reference intake values are set for healthy individuals, and nutrient requirements are likely to be differ in disease.

3.5 Insulin and glucose responses to food consumption

Following food consumption, absorbed carbohydrates give a rise in blood glucose concentrations. In response insulin is released causing blood glucose to fall. Different food components evoke different responses e.g. simple sugars give both rapid increases and falls. Glucose response refers to the degree of rise and fall in blood glucose levels and the time interval within which it occurs. Slowly digestible carbohydrates show a slower and more prolonged increase in blood glucose levels (with a lower peak) and vice versa. The glycemic index (GI) shows the average glucose concentration in the blood after consumption of a certain food (usually for 2 hours) relative to a standard food. The test foods usually contain 50 grams (or 25 grams if portion size is very large) of available carbohydrate and the reference food (anhydrous glucose powder, 50g or dextrose, 55g) has a GI of 100 [45]. Available carbohydrate of a food is estimated by difference: $100 - \text{water (g/100 g EP)} - \text{total fat (g/100g EP)} - \text{total protein (g/100 g EP)} - \text{total dietary fibre (g/100 g EP)} - \text{ash (g/100 g EP)}$. The GI is obtained from the area under the 2hour curve (iAUC)¹ [46] as:

$$\frac{\text{iAUC of the test food}}{\text{individual subjects/average iAUC of the reference food}} * 100$$
. Overall GI is calculated as mean (\pm SEM) GI value for ≥ 10 participants. From the GI, the glycaemic load (GL) can be derived. It is calculated

¹ The incremental area under the curve has been calculated as the incremental area under the blood glucose response curve (iAUC), ignoring the area beneath the fasting concentration. This can be calculated geometrically by applying the trapezoid rule. When a blood glucose value falls below the baseline, only the area above the fasting level is included.

as: $\frac{GI}{\text{Total available carbohydrate in the food portion}}/100$. GI gives information on glycaemic quantity as a factor of food portion size, and may be used as an indicator of insulin demand.

Insulin release can be triggered by other food components such as proteins and fats. The food insulin index (FII) allows for testing of foods with no or low carbohydrate content. It shows the observed (plasma) insulinemic response to consumption of a particular food compared to an isocaloric portion of the reference food over a 2 hour period. It is obtained as: $\frac{\text{iAUC for 1000kJ test food}}{\text{iAUC for 1000kJ reference food}} * 100$. FII has previously been reported to have potential of reducing postprandial hyperinsulinaemia in T2DM management [47].

4. RESEARCH OBJECTIVES

4.1 General objective

1. To assess the appetite, insulin and blood glucose responses associated with consumption of an acceptable novel common bean product

5. CONCEPTUAL FRAMEWORK AND OPERATIONALIZATION

5.1 Conceptual framework

Common beans in type 2 diabetes patients could have many health benefits such as modulation of glucose metabolism, reduction of low density lipoproteins, and satiety [48,49]. The conceptual framework (Fig. 1) we have adopted proposes that short term metabolic responses are a factor of baseline characteristics of an individual, common bean product portion and feeding frequency [50].

[figure not shown]

Figure 1: Conceptual framework on how common beans can increase nutrient intake, and potentially improve metabolic responses in T2DM patients

For T2DM patients, portion control is one of the pillars in dietary management. Based on the main ingredient (common bean), form (solid), nutrient composition (available carbohydrate, fibre and protein) and oral processing needed (high sensory exposure/chewing time), we aim to develop a product that is highly satiating. The portion will also be influenced by the product packaging size of approximately 150-200 grams.

The frequency and timing of the common bean product is also key. From the baseline study, majority of the T2DM were between 40-69 years. Age is associated with loss of appetite. In such a population group, small portions and frequent meals are recommended. We aim to provide a product that allows for optimization of the intake of vitamins and minerals in adults [48, 49].

5.2 Operational definition of variables

For the assessment of metabolic responses associated with consumption of the common bean product, Figure 2 below illustrates the relationship between the dependent (blood sugar, insulin) and independent variable (common bean product consumption):

[figure not shown]

Figure 2: Factors influencing glyceimic and insulimemic responses

Recent evidence suggests that CRP levels are higher in people with diabetes compared with those without diabetes. However, less is known about whether CRP in people with diabetes is related to level of glyceimic control. Poor glyceimic control is significantly associated with the development of macrovascular complications of diabetes. We will be using the CRP data to evaluate association with glyceimic control in this particular population. The lipid profile, dietary intake and bio-electrical impedance data are some of the variables that will be used to explain observed blood glucose and insulin measurements.

6. HYPOTHESES AND RESEARCH QUESTIONS

6.1 Hypotheses

H1: the new common bean product is not associated with desirable satiety, glyceimic and insulimemic responses in the T2DM patients.

6.2 Research questions

1. What are the post prandial insulin, blood glucose and appetite responses associated with consumption of the common bean product in:
 - a. healthy volunteers?
 - b. T2DM patients?

7. STUDY DESIGN AND SAMPLING STRATEGY

7.1 Glyceimic index (GI) and glyceimic response study

The GI evaluates the blood-raising ability of equi-carbohydrate portions of different single foods or mixed meals. To assess the GI of the common bean product *in vivo*, 10 healthy volunteers will be recruited. The selection of the number of participants, and the inclusion and exclusion criteria is based on the ISO_26642_2010 standard [53].

The 10 healthy volunteers will be recruited from Jomo Kenyatta University of Agriculture and Technology (JKUAT) and handled at the JKUAT University Hospital.

Inclusion criteria:

- Male or female 18-69 years
- No known food allergies or intolerances
- No prescription medication² (excluding oral contraceptives) known to affect glucose intolerance (e.g. steroids, protease inhibitors, antipsychotics e.t.c.)

Exclusion criteria

- Known history of diabetes mellitus or use of anti-hyperglycaemic medication or insulin
- Alcohol or tobacco use in the evening preceding the test
- Vigorous exercise on the morning of the test
- Undergone major medical/surgical event needing hospitalization within the preceding 3 months
- Presence of disease or drug influencing digestion and absorption of medicine

Glycemic response associated with consumption of the common bean product will be assessed in 10 T2DM patients in Makueni County. The participants will be recruited from the **Makueni Level-5 and Mbooni sub-county hospitals** which run a diabetes outpatient clinic.

Inclusion criteria:

- Male or female aged 18-69 years
- Previously diagnosed with type 2 diabetes
- Consenting to participate

Exclusion criteria:

- Use of prescription medication
- History of eating disorders and irregular eating habits
- Use of tobacco or alcohol
- Females experiencing menstrual period or adverse premenstrual symptoms

For the reference food, we will use either anhydrous glucose powder, 50g or dextrose (glucose monohydrate), 55g. The reference food will be dissolved in 250ml of water and refrigerated for use within 72 hours after preparation. Participants will be fed with an equi-carbohydrate portion of the common bean product to the reference food.

² Stable doses of oral contraceptives, acetylsalicylic acid, thyroxin, vitamins and mineral supplements or drugs to treat hypertension or osteoporosis are acceptable

The GI of the food will be measured over a 120 min period starting at the ingestion of the common bean product. The test food and reference food will be assessed in each subject on separate days with a 1 week period between each study day.

The GI value of the common bean product will be calculated as follows: = [iAUC of the common bean product/individual subject's average iAUC of reference food]*100. The overall GI will then be obtained as: The mean GI value for the 10 participants.

The test conditions, sample size and methodology are as adopted from the international standard ISO 26642:20110(E)³ [53].

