7.2 Food insulin index (FII) and insulin response

To assess the FII of the common bean product *in vivo*, 10 healthy volunteers will be recruited from Jomo Kenyatta University of Agriculture and Technology. Insulin response associated with consumption of the common bean product will be assessed in 10 T2DM patients in Makueni County. Participants will be fed with iso-caloric (240 kilocalorie) portions of the test food and reference food.

Inclusion and exclusion criteria for the FII and insulin response used will be as cited in GI study (see section 7.1).

The FII of the food will be measured over a 120 min period starting at the ingestion of the common bean product. The test food and reference food will be assessed in each subject on separate days with a 1 week period between each study day.

The FII value of the common bean product will be calculated as follows: = [iAUC of the common bean product/individual subject's average iAUC of reference food]*100. The overall FII will then be obtained as: The mean FII value for the 10 participants.

³ The standard was issued under licence to [name] (co-principal investigator)

Insulin response associated with consumption of the common bean product will be assessed in 10 T2DM patients in Makueni County.

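### Does the T2DM medication exclusion in Section 7.1 need changing because it does not say whether footnote 2 applies to it?

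*Combined protocol and SAP*

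**What the plan says.** Section 7.1 has separate eligibility lists for the 10 healthy volunteers and the 10 T2DM patients.

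- **Healthy volunteers.** The medication criterion is limited to prescribed drugs "known to affect glucose intolerance (e.g. steroids, protease inhibitors, antipsychotics e.t.c". It carries the marker for footnote 2, which reads "Stable doses of oral contraceptives, acetylsalicylic acid, thyroxin, vitamins and mineral supplements or drugs to treat hypertension or osteoporosis are acceptable".
- **T2DM patients.** One exclusion is "Use of prescription medication". It has no qualifier and no footnote marker.

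Section 7.2 carries the criteria over to the insulin work: "Inclusion and exclusion criteria for the FII and insulin response used will be as cited in GI study (see section 7.1". Appendix 2, questions 1 to 3, matches the other three T2DM exclusions. Question 5 asks about any current medication and takes down the drug, timing, dose and maker.

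Section 1 describes the sponsor's 2018 survey of T2DM patients (N=168): "72.2% of the participants were also" "hypertensive (reported current use of hypertension medication".

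**The concern.** Both lists use the same term for prescribed drugs, and footnote 2 names no group. A reader could take it as defining the term throughout Section 7.1, or as belonging only to the line where it is marked. The two readings give opposite answers for a T2DM patient whose only prescribed drug is a stable antihypertensive, and the survey suggests such drugs are common locally.

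What would be at stake is whom the 10 patients represent. Section 5.1 holds that "short term metabolic responses are a factor of baseline characteristics of an individual", and Section 1 says "This product profiling is key to inform dietary management of T2DM patients using this specific product". If staff at the two recruiting hospitals read the rule differently, the T2DM group would be a mixture that no one had specified. Question 5 does not ask whether a drug is prescribed (needed for the strict reading) or whether its dose is stable (needed for the permissive one).

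**Working it through.** **Inputs.** Antihypertensive use 72.2% and survey N=168 (Section 1); 10 T2DM patients (Section 7.1); enumerator numbers (Section 12.3).

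**1. The survey figure.** 121/168 = 72.0% and 122/168 = 72.6%, so no whole count out of 168 gives 72.2%. A smaller denominator would (117/162 or 109/151, for example). The documents do not state one, so 72.2% is used as printed.

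**2. Strict reading.** Antihypertensive users among the 10: 0, by rule. If all reported use is of prescribed drugs, the share not excluded on this ground is 1 − 0.722 = 0.278. About 10/0.278 = 36 patients would be screened to find 10, before any other exclusion.

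**3. Permissive reading.** Expected users are 10 × 0.722 = 7.22. Under Binomial(10, 0.722) the central 95% range is 4 to 10, and P(none) = 0.278^10, about 0.000003. This assumes that eligible patients use antihypertensives at the survey rate and that all doses are stable. Other assumed rates give:

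| Assumed rate among eligible patients | Expected of 10 | 95% range |
|---|---|---|
| 30% | 3 | 0 to 6 |
| 50% | 5 | 2 to 8 |
| 80% | 8 | 5 to 10 |

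**4. Other prescribed drugs.** Footnote 2 lists no glucose-lowering drugs, so a patient prescribed one is excluded on either reading. Let g be the share of patients on any other excluding prescribed drug, taken as independent of antihypertensive use. The documents give no value, so g is assumed. The eligible share is 0.278(1 − g) on the strict reading and 1 − g on the permissive one.

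| g | Strict | Permissive |
|---|---|---|
| 0% | 27.8% | 100% |
| 50% | 13.9% | 50% |
| 95% | 1.4% | 5% |

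If g is high, eligibility is narrow either way and the footnote is a secondary question.

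**5. Effect on the mean response.** The eligible patients' mean differs from the mean of all patients by the excluded share times the difference between eligible and excluded patients. With 10 patients the standard error is SD/√10 = 0.316 SD. At 72.2% excluded, a difference of 0.316/0.722 = 0.44 SD would be needed to move the mean by one standard error. No input in the documents suggests a difference of that size, or any difference.

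**6. Who applies the rule.** Section 12.3 pays for training 2 enumerators and for 8 enumerator-days over 4 days: 8/4 = 2, a single pair. Section 8.2 has the research team train them, including in how questions are to be interpreted, and assess their competence.

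**7. What the form settles.** A negative answer to question 5 satisfies both readings. A positive one comes with the drug and dose, which usually identifies the class. Only prescription status and dose stability are missing.

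**The case for a change.** The strongest case for a change is that clarification is cheap before recruitment and cannot be fully recovered later. Both readings can be defended: the term is shared, the footnote is silent on group, and Section 7.1 rests its eligibility criteria on one ISO standard. At the survey rate the two readings give clearly different samples. If the strict rule is intended, it excludes most patients like those surveyed, and no reason is given. If it is not intended, the line is misprinted. A count of patients screened out, by drug class, would be hard to reconstruct afterwards.

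Part of this stands. The text does not say whether the footnote was meant to extend to the T2DM list, question 5 lacks two items, and the denominator of the 72.2% is unstated. Section 7.1, its footnote and question 5 should be read together and reconciled by the investigators.

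The rest is weaker. The readings are not equally supported, because marker placement and the separate, unqualified T2DM line favour the strict one. One trained pair of enumerators makes divergence between hospitals unlikely. The documents list Appendix 2 under data collection and never call it a screening form, so its gaps say little about how eligibility is decided. A tally of exclusions would be informative, but it is a reporting preference; the planned results do not depend on it.

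**Conclusion.** No change to the plan follows. The printed rule can be followed as it stands, and the permissive reading is an inference from a shared term. The contrast of 0 against about 7 of 10 (range 4 to 10) is arithmetically right. It depends on survey users taking prescribed drugs at stable doses, and on the survey rate holding among eligible patients. The survey is not stated to come from the recruiting clinics or from the 18 to 69 age range.

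On either reading the glucose and insulin responses are sound for the patients enrolled. The effect on the mean is unknown and possibly nil, and no loss of generalisability can be quantified from the documents. Confirming the intended scope of footnote 2 is a detail the team can settle when training its enumerators. The drug details from question 5 let the report state which T2DM patients were studied. Which medicines to allow is for the investigators.
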